22.3 Risk from wearable repellent technologies

Wearable repellent technologies will be formulated to contain insect repellent at doses within published limit of safe application. Because the repellent product will be formulated into plastic, most likely low density polyethylene (LDPE) or high density polyethylene (HDPE), the amount of product that is released onto the skin will be considerably lower than that which is experienced via topical application of a cream.

22.4 Burden associated with participation

22.4.1 Laboratory trials

Participants will be required to make repeat visits to the LSHTM testing facility, to test each product and product formulation. During visits, they will be required to sit still for ten-minute observation periods, allowing flies to crawl freely over their forearm and hand.

22.4.2 Field trials

The participant's face will be observed and filmed for ten-minute periods. During this time, the participant will be required to sit motionless and allow flies to crawl freely over their face and around their eyes, nose and mouth. In this study setting this burden would be considered 'the norm', with children rarely bothering to brush away flies due to their extreme persistence and prevalence.

At the first time-point of testing, the child will be asked to sit for ten minutes of control measurements, immediately followed by ten minutes of test measurements, with the application of insect repellent in-between. Ten-minute duration follow-up sessions will be conducted hourly for the rest of the day (six hours). As participants may be as young as three years old, sitting motionless for these periods may be difficult, additionally, the child may become distressed.

We will encourage the children to conform to protocol as far as possible but will make reasonable judgement around levels of distress. To be, and remain, eligible for the field trial, we state "15. The participant does not become unacceptably upset during the procedures". The same methodology 'Fly-eye studies' are currently underway as part of the Stronger-SAFE Phase 1 study of Ct transmission in the same study site. In Phase 1, the team are conducting 'Fly-eye studies' on two children in each of more than 200 households, and as such have gained a great amount of experience in this type of work. The Phase 1 'Fly-eye studies' constitute two components, the ten-minute observation/videoing period as described above in this protocol, followed by 15 minutes of catching flies from the child's face. So far, we have not observed many instances in which the child becomes upset in the initial ten-minute period, with the latter fly-catching exercise generally proving more difficult. In instances where the child does become upset, the field team tries to calm the child with the help of the primary caregiver, or his/her friends and family, and encourage them to allow work to continue. If the child continues to be upset, sampling/participation is

discontinued for that child. In terms of managing distress, the same protocol will be followed for this study.

22.5 Benefits associated with participation

Participants in the laboratory trial will receive no benefits from participation in the trial. Participants in the field trial will have the opportunity to have their vision and eyes checked by the Stronger-SAFE project team, and will receive appropriate referral for identified problems. There are no further benefits expected for any participants.

23 Modifications

Should it be necessary in the field trials, lower dose topical repellents can be substituted to improve tolerance to the facial application (e.g. in the event of discomfort), provided those lower doses were found to provide at least 30 % protective efficacy.

24 Adherence

24.1 Trial adherence

The critical importance of both participant availability (for data collection), and sustained use of repellents, will be emphasised during recruitment, and participants and their parents/guardians be reminded of the importance of this when giving assent/consent. It is expected that this will present a specific challenge in the field clinical trials, where participants who test the wearable repellent devices will be required for weekly repeat testing of the product over a four-week period. Therefore, in the field trial, the following measures will be implemented:

- ‘Adherence reminder sessions’ will be conducted at each testing time point (e.g. at each visit to the household). The importance of allowing topical repellent to remain on the face (i.e. without washing off or removing in any other way), and of wearing the repellent device, for the full testing duration (six hours or seven days respectively) will be emphasised (Appendix 16, Adherence reminder sessions). This will be of primary importance to the wearable repellent device interventions, as for the topical repellent trials investigators will be present throughout the six-hour duration, and can supervise.
- In the six days between each testing session, for those households contactable by mobile phone, text messages will be sent to remind the primary caregiver to ensure the participant continues to wear the repellent device
- For the four, weekly follow-up testing sessions (wearable repellent devices only), on the day prior to testing one of the fieldworkers will visit the household to remind the participant’s primary caregiver that the child should remain at home the following day for testing. During these ‘priming’ visits, the fieldworker will also discretely note whether the child is wearing the device or not, but will not comment on this or draw attention to their assessment.
- On days in-between those four weekly follow-up sessions, a limited number of unannounced visits by a member of the project team may take place to allow an

opportunity for problems relating to repellent use to be identified and addressed. Participants will be informed about the possibility of those visits at recruitment and during consenting.

24.2 Trial adherence assessment

Adherence to the protocol in the laboratory clinical trial will be simply recorded as participant presence/absence for follow-up testing.

Adherence to the protocol in the field clinical trial will comprise either: (1) wearing the topical repellent on their face for the full testing duration of six hours, or (2) wearing the repellent device for four consecutive weeks.

Adherence to protocol for topical repellents can be monitored and recorded by the field team, who will be present for the full six hours of testing. Adherence to the protocol for wearable repellent device use after the initial testing day (when the field team will be present) will be assessed by recording whether or not the participant is wearing the device at the time of each data collection visit, and at the time of each 'priming' visit on the day prior to testing. At each visit, participants will also be asked to report on any difficulties faced in continued use of the device.

25 Comparability of study groups (concomitant insect-repelling activities/factors)

Co-intervention bias is precluded in the laboratory trial by the trial design being within-subject.

To mitigate external influences on the outcome variables (frequency of fly contacts), participants in all trials will be asked to refrain from the use of any perfumed or scented product, including bathing products, for a 24-hour period before each testing session.

In the laboratory trial, co-intervention bias will be mitigated by asking participants to refrain from using any insect repellent products for a 48-hour period prior to any testing session.

In the field trial, co-intervention bias will be mitigated by asking participants and their families to refrain from the use of any insect-repelling activities for the duration of the trial. Previous observational work in the region has identified only one such activity, which involves scattering the leaves of *Schinus molle* trees on the floor and hanging these by the door. The leaves of this tree are considered to have anti-fly properties, although this belief is unsubstantiated.

26 Data

26.1 Data collection

26.1.1 Laboratory trials

Data to be collected are: Participant name and ID number, address, phone number and email address, confirmation of informed consent, date of birth, eligibility details, topical repellent skin test details (active ingredient, amount, 24 h assessment), visit details (date and time of visit to

testing facility, investigator conducting testing, person variables [body weight, tympanic temperature], temperature and humidity of testing room, repellent product and concentration tested, testing variables [Number of *Musca sorbens* flies, number of different sex, age of flies, video file ID] and adverse event monitoring).

All arm-in-cage observation and videoing will be conducted by the laboratory co-PI or GCP trained staff, as will application of the repellent product. All investigators involved in the trial will be trained in the study requirements and will follow standard operating procedures, to ensure each participant is studied in a uniform and reproducible manner.

26.1.2 Field trials

Data to be collected are: Participant, household and kebele name and ID number, phone number, woreda name, confirmation of informed consent, date of birth, eligibility details, topical repellent skin test details (active ingredient, amount, 24 h assessment), visit details (date and time of visit, fieldworkers conducting testing, person variables [ocular or nasal secretions, body weight, tympanic temperature], environmental conditions, repellent product and concentration tested, number of fly-eye, -nose, -mouth and -face contacts, video recording of face), adverse event monitoring and qualitative data from the end-of-trial product acceptability interviews.

All fly-eye observation and videoing will be conducted by trained entomological fieldworkers with experience in fly-eye studies. Application of the repellents will be conducted by qualified ophthalmic nurses. All fieldworkers involved in the trial will be trained in the study requirements and will follow standard operating procedures, to ensure each participant is studied in a uniform and reproducible manner.

26.2 Data management and confidentiality

All data will be protected and stored in compliance with General Data Protection Regulation (GDPR). Specifics per site are given below.

During screening, participants will view the participant screening form (PSF, see Appendix 17) as it is being completed. During screening and testing, all data collected (during both laboratory and field trials) will be recorded at the time of collection via electronic data capture using the Open Data Kit (ODK) secure data capture system provided by LSHTM <http://opendatakit.lshtm.ac.uk/>. The PSF and data collection forms will be created and managed in ODK, and study participants will not view the data collection forms. Automatic checks for invalid values, internal consistency and implausible responses will be programmed into ODK, and additional data validation checks will be run after data collection. ODK has an inbuilt audit trail. Encrypted data will be uploaded to a secure server at LSHTM for secure storage and analysis. Daily back-up of study data on central computers and servers, remote computers and hand-held devices will be conducted. Back-up data will be stored separately from the primary electronic storage, and video files (showing the participant's arm or face for laboratory or field trials respectively) will be stored on encrypted external hard drives, or encrypted and uploaded to LSHTM secure server.

After study completion, all the relevant study documentation will be retained in accordance with the local legislation, for a minimum period of 10 years after completion of the study. The final dataset will be archived and maintained by the UK PI. Anonymised data sets will be made publicly

available after publication, to ensure the data are available for other investigators to explore. Specific permission for this is requested in the consent form.

26.2.1 Laboratory trials

Data from the study will be managed by the LSHTM PI. Paper records (Informed consent/assent, PSF, adverse event monitoring questionnaire, adverse event record) will be stored in locked cabinets in the locked Arctec office in LSHTM. Scanned electronic back-ups of these will be encrypted and uploaded to LSHTM secure server.

26.2.2 Field trials

Data from the study will be jointly managed by the LSHTM and Stronger-SAFE team in Ethiopia, coordinated by the UK and Ethiopian PIs. Paper records (Informed consent/assent, PSI, adverse event monitoring questionnaire, adverse event record) will be stored in locked cabinets in the secure/locked Stronger-SAFE project office. Scanned electronic back-ups of these will be stored in encrypted external hard drives, kept separately in the same office.

The UK and Ethiopian PIs will be responsible for ensuring a secure and appropriate location for storage of study related documentation present at the field study site, as well as for ensuring that only members of site staff who are authorised have access to the files. The site Investigator File will be held at the project office in Shashemene. The Investigator File will at all times remain available for internal audits and/or inspections of regulatory authorities, including after completion of the project.

26.3 Data analysis

26.3.1 Protective Efficacy, p

The protection (protective efficacy, p) afforded by a repellent product will be presented as a percentage. p will be estimated by comparing fly-arm contact duration and fly-eye contact frequency, in laboratory and field trials respectively, after application (or wearing) of the repellent product to that during the control period.

Equation 1. Protective Efficacy, p

$$p = 100 \times ((C - T)/C)$$

Where (laboratory trials):

- C is the total duration of fly-arm contact before application of repellent ('control' measure), and
- T is the total duration of fly-arm contact after application of repellent ('treatment' measure)

Where (field trials):

- C is the frequency of fly-eye contacts before application of repellent ('control' measure), and

- T is the frequency of fly-eye contacts after application of repellent ('treatment' measure)

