13.2 Field trial

In the field clinical trial, eligible participants will be randomised between groups (study arms), each of which will test only one topical repellent or slow-release wearable repellent device, at one concentration. A maximum of four groups will be tested in addition to a control group, and each group will contain 29 children between the ages of three and 12 years. The additional control group, receiving no product, will allow for temporal comparison of fly contact across a day of testing.

The combination of product and product format to be tested will be determined before the study commences. The PE will be determined by measuring the frequency of fly-eye, fly-nose, fly-mouth and fly-face contacts by *Musca sorbens* after application of the product, in a 'field' environment where these flies are naturally present at high density. Control measurements will be taken of fly contact on each participant prior to this. Test measures will be repeated over a period of six hours to determine the ET_{50} , and for wearable repellent devices, participants will continue to wear the

product and tests will be repeated at one, two, three and four weeks later. Topical repellents will be applied by the Stronger-SAFE field team nurses, who will also demonstrate how to wear the repellent devices. A qualitative assessment of acceptability and barriers to use will be carried out at the end of the trial.

14 Study setting and populations

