17.2 Secondary outcome measures

1. Median Complete Protection Time (mCPT) in laboratory trials only
2. Median Effective Dose (ED₅₀), in laboratory trials only
3. Median Effective Time (ET₅₀), in both laboratory and field trials
4. Acceptability of the repellent interventions among children and their caregivers, in field trials only

18 Participant timeline

A timeline of participant recruitment and enrolment, consent, and completion of the clinical trials is given in Figure 4.

Figure 4. Participant timeline for clinical trials of insect repellents against fly contact by *Musca sorbens*

19 Sample size

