19.2 Field trials sample size

This trial will be powered to detect a protective effect in the intervention (treatment) groups relative to the control groups. To test for 30 % protection (PE) in the intervention arm versus the control arm, assuming a standard deviation of 30% and using 90 % power, 23 children are required in each study group. When allowing for 25 % loss-to-follow-up, the total sample size in each study arm will be 29 people. Equal numbers of male and female participants are preferred.

Not all approximately participants in the wearable repellent device arms of the field trial will be interviewed for intervention acceptability. Based on previous experience, we anticipate that a sample of 15 to 20 child-caregiver pairs, purposively sampled to represent the range of child ages will be sufficient, and further data collection unlikely to yield additional information. However, we will review our data regularly during the data collection process and will adjust the sample accordingly.

20 Enrolment, randomisation and allocation

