20.2 Field trials

Prior to approaching members of the communities in which we wish to work there will be initial dialogues with the community leaders and local health officials to introduce the purpose and nature of the research project. Following this, participants will be recruited by visiting households in the study site that are home to children in the correct age bracket. Information about the study will be shared with potential participants by members of the field research team, who have previous experience in the participant information and consenting processes. During the visit, participants will be provided with Information Sheets (Appendices 4 and 5), a Product Information Sheet (Appendix 6) and Informed Consent and Assent forms (Appendix 7). Assent will be sought from the participant, and consent from the primary caregiver. This will be in Afaan Oromo, the

regional language. This will be read to those who are unable read. After verbal explanation of the relevant sections of the Information Leaflet and having the opportunity to ask questions, informed consent will be gained and evidenced by a signature or thumbprint signature (deemed acceptable locally due to high rates of illiteracy), in the presence of the study team and independent witness.

Eligible participants will be randomised equally between the topical repellents and wearable repellent devices found to be protective in laboratory clinical trials, and a control group receiving no intervention.

21 Study procedures

This clinical trial encompasses a series of laboratory studies, designed to determine which of a number of commercially available repellents provide protection against laboratory-reared *Musca sorbens* fly contact, followed by a field trial testing the protection afforded by these repellents and wearable repellent devices, from fly contact by wild *M. sorbens* on children aged three to 12 years. In the field trials, the acceptability of these products to the end-users (both children and their caregivers) will be assessed.

Prior to both trials, preliminary benchmarking laboratory studies will be conducted to determine which of five repellent actives will be studied in the clinical trials.

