26.3.3 Median Effective Dose (ED₅₀) and Median Effective Time (ET₅₀)

ED₅₀ and ET₅₀ will be calculated in stage two ('persistence') laboratory trials, however, as only one dosage level will be used in the field only ET₅₀ will be estimated there.

The relationship between Protective Efficacy and repellent dose and time since treatment can be estimated using a probit-plane regression model (Equation 2). The coefficient b_1 provides an estimate of the effect of repellent dose on p , and b_2 provides the effect of the time since treatment on p .

Once these coefficients have been estimated, then we can estimate the ED₅₀, concentration (dose) of repellent product that affords 50 % protection from fly contacts at time zero (the time of application). This is done by setting $p=0.5$ and $t_1=0$ and then solving equation 2. We can also estimate ET₅₀, estimating the persistence of the protective effect of a repellent product for a given dosage, using the same method.

Equation 2. Probit-plane regression model for ED₅₀ and ET₅₀

$$\ln [p / (1 - p)] = a + b_1(D_0) + b_2 t_1$$

Where:

- p is as above, estimated from
 - Total duration of fly-arm contact (laboratory trials)
 - Total frequency of fly-eye contacts (field trials)
- D_0 is the dose calculated as the natural logarithm of the dose applied ($\ln[\text{dose}]$)
- t is the time post-treatment in hours
- a , b_1 and b_2 are coefficients estimated using the probit-plane regression model

In the laboratory trials, p will be estimated by the total duration of fly-arm contact, while in the field trials p will be estimated using the total frequency of fly-eye contacts, as defined in section 26.3.1.

27 Monitoring

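### The field analysis in 26.3 never uses the randomised no-product arm, so later first-day field PE and the first-day ET50 absorb any time-of-day change in fly activity

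*Combined protocol and SAP*

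**What the plan says.** **Role given to the arm.** Section 13.2: "The additional control group, receiving no product, will allow for temporal comparison of fly contact across a day of testing". Section 20.2 allocates eligible children equally to the products "and a control group receiving no intervention". Section 19.2: "This trial will be powered to detect a protective effect in the intervention (treatment) groups relative to the control groups". It arrives at 23 children per group, raised to 29 for loss to follow-up.

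**First-day schedule.** Testing starts between 09:00 and 10:00 (21.2.1). Each child has one control period, a test straight after application, and five further hourly tests (21.2.3, 21.2.4).

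**Analysis.** Section 26.3.1 compares contact "after application (or wearing) of the repellent product to that during the control period". For the field, Equation 1 states that "C is the frequency of fly-eye contacts before application of repellent". In Equation 2 the time term is defined as "t is the time post-treatment in hours". Neither equation has a term for arm or clock time, and 26.3 describes no comparison with the no-product arm.

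**Use of the results.** ET50 is a secondary outcome "in both laboratory and field trials" (17.2). Section 16.2.2 says that field PE and the other field outcome measures will inform which repellents enter the Phase 3 RCT.

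**The concern.** A child's later counts can change because the repellent is wearing off or because background fly activity has changed since the control slot. Equation 1 attributes the whole change to the repellent. If background activity rises through the day, a product looks shorter-lived than it is; if it falls, longer-lived.

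The no-product arm is the part of the design that can tell these apart, and 13.2 says that is its purpose. An analyst who followed 26.3 exactly would never open its data. Nor would that analyst make the between-arm comparison for which 19.2 calculated the 23 per group. Without a prespecified step, the use of the arm would be decided after the data are seen.

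**Working it through.** **1. What the 23 was calculated for.** Inputs from 19.2: difference 30 points, SD 30, power 90%. Alpha is not stated; two-sided 5% is assumed.
- Two-sample normal formula: 2 × (1.960 + 1.282)² × (30/30)² = 21.0. The two-sample t-test needs 22.02, so 23 per arm (power 91.2%). This reproduces the plan's figure.
- A within-child (one-sample) t-test would need 12.59, so 13.

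The 23 therefore comes from a between-arm comparison, which 26.3 does not contain.

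**2. Overlap of time since application and clock time within an arm.** Assume starts spread evenly over the one-hour window and tests at 0, 1, …, 5 h. The variance of hours since application is 35/12 = 2.917, and that of start time is 1/12 = 0.083. Correlation = √(2.917/3.000) = 0.986, and variance inflation = 3.000/0.083 = 36. The confounding within an arm is near-complete, though not exact.

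**3. Effect on hourly PE.** Let m be background contact at the later hour divided by background at the control slot. Equation 1 then returns 1 − (1 − PE) × m. The documents give no value for m, so a range is assumed. For a true PE of 60%:

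| m | 0.7 | 0.9 | 1.0 | 1.1 | 1.25 | 1.5 |
|---|---|---|---|---|---|---|
| PE from Equation 1 | 72% | 64% | 60% | 56% | 50% | 40% |

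**4. Effect on ET50.** Assume a product with p(0) = 0.80 and p(5) = 0.50, so logit p(t) = 1.386 − 0.2773t and the true ET50 is 5.0 h. Let m move linearly from 1 at time zero to M at 5 h. Apply step 3 to each hour and refit Equation 2 by least squares on t = 0 to 5. The field uses one dose, so the dose term merges into the intercept.
- M = 1.1: fit 1.399 − 0.3167t, ET50 = 4.4 h.
- M = 0.9: fit 1.374 − 0.2376t, ET50 = 5.8 h.

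| M | 0.7 | 0.9 | 1.0 | 1.1 | 1.25 | 1.5 |
|---|---|---|---|---|---|---|
| Fitted ET50 (h) | 8.7 | 5.8 | 5.0 | 4.4 | 3.8 | 3.0 |

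The 5.8 and 8.7 h values extrapolate beyond the last observation at 5 h.

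**5. What the no-product arm does.** In that arm T_t/C estimates m. Dividing the product-arm ratio by it gives 1 − [(1 − PE) × m]/m = PE, whatever m is, provided m is the same in both arms.

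**6. Precision of the adjusted estimate.** Simulation in which every input is assumed: 4,000 trials, 23 per arm, independent negative binomial slots with shape 2, 5 or 10 and mean 20 or 50 contacts, no drift, true PE 50% at 5 h, ratios of arm totals. The SD of the 5-h estimate is 0.055 to 0.116 unadjusted and 0.075 to 0.169 adjusted.

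**7. Why not a mean difference in per-child p.** Under the same count assumptions, dropping children with C = 0, the expected time-zero difference is 57 to 105 points for a true 50%, because C is a noisy denominator. Independent slots are a severe assumption. With a shared child effect and Poisson slots it is still about 52 to 55. At shape 2 and mean 20 there is a 32% chance that at least one of 46 children has C = 0, where per-child p is undefined.

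**The case against.** The strongest reply is that the intention is already on paper. Section 13.2 states the arm's temporal purpose, 19.2 names the contrast, and 26.1.2 records "visit details (date and time of visit, fieldworkers conducting testing". That stands: the gap is an unwritten estimator. A reader might infer that the trial cannot separate the two effects, or that the control arm will not be observed hourly. The documents support neither. The available text of 21.2 does not state the arm's schedule, but Figures 7 and 8 are not shown and may contain it.

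A second reply is that products tested at the same hour share the drift. This also stands in part. For a given m, 1 − (1 − PE) × m rises with PE, so a trend common to all arms leaves same-hour rankings intact. It does not protect the absolute PE or ET50, which are what 26.3 reports.

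A third reply is that drift is unproven. A reader might take the remark in 21.2.1 that flies are less active earlier as evidence of rising activity, and so of ET50 biased downward. It does not show that: it explains why testing starts at 09:00-10:00 and is silent on what happens afterwards.

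Finally, a reader might extend the problem to the primary endpoint as a whole. Time-zero PE has its control immediately before it (22.4.2), and weekly wearable visits have a same-visit control after device removal (21.2.4), which the lead sentence of 26.3.1 covers. Neither is affected.

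**Conclusion.** The point holds for absolute PE at later first-day hours in the field and for the ET50 derived from first-day data. As written, 26.3 attributes any time-of-day change in fly contact to the product, and it omits both the temporal comparison promised in 13.2 and the between-arm comparison sized in 19.2.

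The size and sign of the bias are unknown. On the assumed curve (time-zero PE 80%, true ET50 5.0 h), a 10% change in background by 5 h moves the fitted ET50 by 0.6 to 0.8 h. With no drift there is no bias. The documents do not show that the wrong product would be chosen: 16.2.2 says only that field results inform inclusion, and same-hour rankings survive a common trend. The step should be added before field data are analysed.

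**What to change.** **(a) Section 26.3.1.** For each first-day time point report, with a 95% CI, p_adj(t) = 1 − [(T_t/C in the product arm) / (T_t/C in the no-product arm at the same time)]. Estimate it from arm-level ratios or from a count model with arm, time, arm × time and a child effect. State the assumption that the background trend is common to all arms. Use the same contrast, not a mean difference in per-child p, as the between-arm comparison that 19.2 sizes. Section 19.2 names no time point, so the sponsor should name one. A count model also retains children with no control-period contacts.

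**(b) Section 26.3.3.** Derive the first-day field ET50 from p_adj(t), and state how values at or below 0 are handled, since the log in Equation 2 is then undefined.

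**(c) Section 21.2.** Confirm in the text that the no-product arm is observed on the same hourly schedule as the product arms.

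**Cost.** Amended text in 26.3 and 21.2, and no extra children. Intervals widen: in the assumed scenarios the SD at 5 h rises from 0.055-0.116 to 0.075-0.169, and 19.2 does not guarantee precision at later hours. Drift that differs between arms is not removed. A residual 0.9 or 1.1 times at 5 h would still move a true ET50 of 5.0 h to 5.8 or 4.4 h.
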